## Purpose of the Study and Background

### Purpose of the Study

Migraine is a significant public health problem worldwide, and migraine has considerable personal and social costs, greater healthcare utilization, work absenteeism. Cognitive behavioral therapy, biofeedback and progressive muscle relaxation therapy for migraine are level A evidence-based behavioral treatments for migraine, yet attrition and suboptimal adherence may diminish its impact. Surprisingly little attention has been devoted to understanding factors associated with following physician recommendation to be treated by a therapist trained in these interventions and the role of adherence with these treatments. This study will evaluate factors associated with adherence to referral to behavioral treatment.

## Study Design

This is a prospective study to examine factors associated with adherence to referral for migraine behavioral treatment.

Patients will be recruited from the New York University Medical Outpatient Setting (both in the FGP Neurology Group by neurologists who have large headache practices and in the private practice office). Consecutive subjects presenting with a chief complaint of headaches with migrainous features will be recruited.

Drs. [name], [name], [name], [name], [name], [name] and [name] will be the neurologists recruiting for the study. [name] will begin recruitment on 5/27/16.

All of these neurologists are part of the NYU Langone Headache Center, and are knowledgeable about the study. No printed information will be given to these doctors.

## Characteristics of the Research Population

### Number of Subjects

2000 total subjects; We expect that 200 subjects will be referred to behavioral treatment.

We are requesting to extend enrollment to 2000 people as fewer enrolled participants are being referred for behavioral treatment than was originally anticipated. Those who are not referred for behavioral treatment are no longer eligible, as that is what is being studied.

\*Of note, as of 12/10/19 only about 150 subjects who have been enrolled have been referred for behavioral therapy. We hope to have a total of 60 subjects who are referred to biofeedback (one of the forms of behavioral therapy) take part in this study.

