### Inclusion Criteria

Inclusion criteria are: a) age 16+ years of age; b) primary diagnosis of migraine based on the International Classification of Headache Disorders 3 beta criteria (documentation of migraine confirmed by Board Certified Neurologist)

Patients will be screened for migraine diagnosis on the questionnaire but the diagnosis will be a clinical diagnosis of migraine based on the ICHD 3 beta criteria made by the neurologist during the patient visit.

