### Exclusion Criteria

Exclusion criteria are: a) No phone number to receive a follow-up call.

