1. They will be approached by research assistants based on their indicated chief complaint. Patients presenting with headache will be informed about the study and consented (as described below). Using the information obtained during the visit (clinical history, physical exam and any additional medical records), the Neurologist will confirm after the visit that the diagnosis is migraine. Participants will complete the initial questionnaires on paper or electronically directly into REDCap using an iPad. The questionnaires include: the Migraine Disability Assessment Scale (Lipton et al, 2001), the Migraine Quality of Life (MSQ v2), the Patient Health Questionnaire-8 (PHQ-8), Generalized Anxiety Disorder 7-item (GAD-7) and the Insomnia Sleep Index (ISI), and a brief series of questions regarding the headache frequency and intensity and history of which types of providers were previously consulted for treatment of the headaches. (All questions are attached). The Neurologist or research assistants will record whether the patient was referred for behavioral treatment. Data will then be entered into RedCap by the PI ([name]) or research assistant(s) (who will be listed on the IRB at a later date) if the diagnosis is confirmed to be migraine.

2. Participants will be told that they will receive a series of follow up calls or REDCap emails regarding their treatment. The PI ([name]) or research assistant(s) who will be listed on the IRB at a later date will be the person to make the telephone call/send the email.

Ten call attempts will be made for each participant for each f/u period (month 1, month 2, month 3). If subjects cannot be reached by phone or text, they will be emailed to set up a convenient time for the follow-up phone call or they will be sent the follow-up survey directly via REDCap. The survey will be emailed a second time if the subject does not respond – 5 days after the first attempt.

Separate documents include scripts of any messages or emails for subjects.

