## **Data Analysis and Data Monitoring**

### **Analysis Plan**

Descriptive statistics for all variables will be reported. We will evaluate differences between people who did and did not follow through on behavioral treatment referrals for normally distributed, rank, and nominal psychosocial and migraine-related variables, respectively, and we will examine whether they chose to pursue behavioral therapy with a therapist (Master's or Doctorate level psych trained therapist or a physical therapist trained in biofeedback). The study does not involve us contacting or working with the PTs for the treatment. We will just collect the data from the questionnaire regarding the subjects' perceptions/decision making of whom to see for behavioral therapy. The physical therapists/psychologists may be outside of NYU. Power analysis suggests we have a power of .80 to detect a medium effect size, with a two-sided test and alpha set at .05. Qualitative analysis will include a grounded theory evaluation of responses to open-ended questions regarding adherence to behavioral treatment referral.

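### Does it harm the comparison that referral is made a condition of eligibility in one section but is absent from the criteria and the call rule?

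*Combined protocol and SAP*

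**What the plan says.** All references are to the combined protocol and SAP.

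- **Number of Subjects** gives the target: "2000 total subjects; We expect that 200 subjects will be referred to behavioral treatment". The paragraph that asks for the larger enrolment adds: "Those who are not referred for behavioral treatment are no longer eligible, as that is what is being studied". It also reports about 150 referrals among enrolled patients by 12/10/19.
- **Inclusion Criteria** list "a) age 16+ years of age; b) primary diagnosis of migraine", and referral is not among them. **Exclusion Criteria** have a single item: "Exclusion criteria are: a) No phone number to receive a follow-up call".
- **Methods & Procedures** has patients consented at check-in on their chief complaint, with the diagnosis confirmed after the visit. In the same step, "The Neurologist or research assistants will record whether the patient was referred for behavioral treatment". Data are then entered "if the diagnosis is confirmed to be migraine". On follow-up: "Ten call attempts will be made for each participant for each f/u period (month 1, month 2, month 3". A patient who cannot be reached is emailed or sent the survey through REDCap, with a repeat after 5 days.
- **Analysis Plan** opens with "Descriptive statistics for all variables will be reported" and then compares patients who followed through on a referral with those who did not.

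**The concern.** Eligibility appears in two forms. Under Number of Subjects a patient without a referral is out. Under the criteria, the data-entry rule and the call rule the same patient is in, has data entered, and may receive up to 30 call attempts over three months. Two staff members following different sections would build different cohorts.

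Three things could be at stake. Most of the follow-up effort could go to people who cannot contribute the follow-through outcome, leaving less for those who can. A descriptive table could cover 2,000 people or 200. And because the Analysis Plan does not say that the referral must date from the index visit, a patient first referred later could be pooled with the rest after less time to act on it.

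**Working it through.** **1. Inputs.** Planned enrolment 2,000 and expected referrals 200 (Number of Subjects). Three follow-up periods with ten attempts each (Methods & Procedures). Power .80, two-sided alpha .05, medium effect (Analysis Plan). Assumption: medium means a standardised difference d = 0.5. The documents give no numerical effect, sample size or group split for the power statement.

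**2. The plan's own power figure.** It cannot be strictly reproduced for lack of those inputs. With d = 0.5 and the normal approximation, the number per group is 2 × (1.960 + 0.842)² / 0.5² = 62.8, so 63 per group and 126 in all.

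**3. Share of enrolment not referred.** (2,000 − 200) / 2,000 = 90%. Consent comes before diagnosis, so some of the 2,000 may prove not to have migraine. If that is 10%, 20% or 30% (assumption), the share is 1,600/1,800 = 88.9%, 1,400/1,600 = 87.5% or 1,200/1,400 = 85.7%.

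**4. Share of follow-up outside the comparison.** The 90% carries over only if every non-referred patient is followed like the others. If half of the 1,800 are dropped after the visit, it is 900/1,100 = 81.8%. If all are dropped, as Number of Subjects implies, it is 0%. The documents do not settle where in this range practice falls. Data Storage and Confidentiality mentions provider emails about participants who need follow-up calls, which hints at selective calling.

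**5. Call volume.** The ceiling for the whole study is 2,000 × 3 × 10 = 60,000 attempts, of which 1,800 × 30 = 54,000 would go to non-referred patients. The call rule sets attempts per period, and fewer are needed once a patient is reached, so this is a maximum. Nor is it what a change could still save. About 150 of the 200 referrals had occurred by 12/10/19. At a constant 10% referral rate (assumption), 150 / 0.10 = 1,500 were already enrolled. Of the remaining 500, 450 would not be referred: at most 450 × 30 = 13,500 attempts.

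**6. Effect on the comparison.** Power = Φ(d × √(n₁n₂/(n₁ + n₂)) − 1.960), where n₁ and n₂ count referred patients only:

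| Split of 200 referred | n₁n₂/(n₁+n₂) | Power, non-referred called | Power, non-referred not called |
|---|---|---|---|
| 100 / 100 | 50 | 94.2% | 94.2% |
| 60 / 140 | 42 | 90.0% | 90.0% |
| 40 / 160 | 32 | 80.7% | 80.7% |
| 20 / 180 | 18 | 56.4% | 56.4% |

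The two power columns agree because the 1,800 do not appear in the formula. The split matters, but it does not depend on who else is called.

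**7. Which reading an analyst would take.** Following through on a referral has no meaning for a patient who was not referred, so the Analysis Plan fixes the comparison set by its own terms. Referral status is in the data to select that set. Since consent comes before the neurologist's decision, referral can only be checked after the visit, as the migraine diagnosis is. On that reading the 2,000 is the intake needed to find about 200 referrals, and the sections fit together.

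**The case for a change.** The strongest case for a change is that an eligibility rule should read the same wherever it appears, whatever its effect on the result. Migraine is also confirmed only after the visit and still stands in the inclusion criteria, so timing does not excuse leaving referral out. No section says when or by whom non-referred patients are withdrawn, and people described as ineligible may still be telephoned. That much stands: the text is untidy, and aligning it would do no harm.

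The arguments that would make it a statistical matter do not stand.

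- **Diverted effort.** A two-sample t test at d = 0.5 needs outcomes from 128 of the 200 (64%) at an even split, or 152 (76%) at 30/70, for power of .80. So reach among referred patients matters. But the documents give no team size or call capacity, and email and REDCap back up the calls. Nothing shows that calling others lowers response among the referred.
- **Late referral.** Less time to act would lower observed follow-through if late referrals were pooled. The documents mention no first referral after the index visit, set no window for following through, and give no rate. Any percentage would stack three assumptions.
- **Descriptive tables.** A table states its denominator. Follow-through variables exist only for referred patients, and baseline variables can be shown for either set.
- **Two recorders of referral.** The protocol lets the neurologist or a research assistant record it. No disagreement between them is documented.

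One further conflict is not resolved here. Process of Consent describes serial calls in one group and a single call in another, which does not match the three-period rule. It concerns the call schedule rather than who is eligible, and it also means that the 60,000 ceiling applies only one of two stated schedules.

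**Conclusion.** The inconsistency exists, but no change to the plan follows. It reads as an eligibility sentence, written with the request to extend enrolment, that was not carried into the other sections. The gap is one that analysts fill correctly from the Analysis Plan and the recorded referral status.

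Its possible size is a workload range: from 0% of follow-up outside the comparison, if non-referred patients are dropped after the visit, to about 90% if all are followed (86% to 89% if 10% to 30% lack confirmed migraine, an assumption). Its effect on the bias and power of the comparison among referred patients is nil, provided that reach among those patients does not depend on how many others are called. The documents give no reason to think that it does. The power figures assume d = 0.5 and an outcome from all 200 referred patients; other values would change them equally under both readings.

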### Gender of Subjects

Both genders will be included.

### Age of Subjects

16+

### Racial and Ethnic Origin

No enrollment restrictions.

### Inclusion Criteria

Inclusion criteria are: a) age 16+ years of age; b) primary diagnosis of migraine based on the International Classification of Headache Disorders 3 beta criteria (documentation of migraine confirmed by Board Certified Neurologist)

Patients will be screened for migraine diagnosis on the questionnaire but the diagnosis will be a clinical diagnosis of migraine based on the ICHD 3 beta criteria made by the neurologist during the patient visit.

### Exclusion Criteria

Exclusion criteria are: a) No phone number to receive a follow-up call.

## Vulnerable Subjects

We are including age 16+. These treatments are appropriate for children and without significant side effects. A recent paper by Scott Powers et al in JAMA showed that the combination of amitriptyline and CBT resulted in the most favorable reduction in headache days.

## Methods & Procedures

### Methods & Procedures

Please note that “RA” stands for study research team member. We carefully select from a group of specially selected group of CUNY students who are part of the highly coveted S Jay Levy Fellowship. These students are pre-selected by CUNY for their professionalism and top grades and then the students undergo a very selective interview process by [name]. We also take high achieving Barnard students who are pre-health who have high grades and many of whom are part of the Barnard Summer Research Institute. [name] has been a mentor as part of this program for several years, and the students in this program are supposed to learn research methods from start to finish, culminating in a poster presentation at a minimum. All study team members will have undergone a one week training intensive to understand the screening process, recruitment process, informed consent process and enrollment process (as described throughout this IRB). In brief, research volunteers will be trained during an intense one week training on study procedures including an emphasis on how to screen, recruit, consent, and enroll the participants. This is a no risk/very low risk study unlike other interventional studies. It is similar to many of the hundreds of commercial apps available on the market that people use every day. Thus, it is appropriate for trained research volunteers to consent these participants just as they would be able to do so for survey type studies. They study team members will be carefully observed during the initial consent process to ensure that they are doing it correctly.

When patients check in and complete their regular intake questionnaire:

1. They will be approached by research assistants based on their indicated chief complaint. Patients presenting with headache will be informed about the study and consented (as described below). Using the information obtained during the visit (clinical history, physical exam and any additional medical records), the Neurologist will confirm after the visit that the diagnosis is migraine. Participants will complete the initial questionnaires on paper or electronically directly into REDCap using an iPad. The questionnaires include: the Migraine Disability Assessment Scale (Lipton et al, 2001), the Migraine Quality of Life (MSQ v2), the Patient Health Questionnaire-8 (PHQ-8), Generalized Anxiety Disorder 7-item (GAD-7) and the Insomnia Sleep Index (ISI), and a brief series of questions regarding the headache frequency and intensity and history of which types of providers were previously consulted for treatment of the headaches. (All questions are attached). The Neurologist or research assistants will record whether the patient was referred for behavioral treatment. Data will then be entered into RedCap by the PI ([name]) or research assistant(s) (who will be listed on the IRB at a later date) if the diagnosis is confirmed to be migraine.

2. Participants will be told that they will receive a series of follow up calls or REDCap emails regarding their treatment. The PI ([name]) or research assistant(s) who will be listed on the IRB at a later date will be the person to make the telephone call/send the email.

Ten call attempts will be made for each participant for each f/u period (month 1, month 2, month 3). If subjects cannot be reached by phone or text, they will be emailed to set up a convenient time for the follow-up phone call or they will be sent the follow-up survey directly via REDCap. The survey will be emailed a second time if the subject does not respond – 5 days after the first attempt.

Separate documents include scripts of any messages or emails for subjects.

## **Data Analysis and Data Monitoring**

### **Analysis Plan**

Descriptive statistics for all variables will be reported. We will evaluate differences between people who did and did not follow through on behavioral treatment referrals for normally distributed, rank, and nominal psychosocial and migraine-related variables, respectively, and we will examine whether they chose to pursue behavioral therapy with a therapist (Master's or Doctorate level psych trained therapist or a physical therapist trained in biofeedback). The study does not involve us contacting or working with the PTs for the treatment. We will just collect the data from the questionnaire regarding the subjects' perceptions/decision making of whom to see for behavioral therapy. The physical therapists/psychologists may be outside of NYU. Power analysis suggests we have a power of .80 to detect a medium effect size, with a two-sided test and alpha set at .05. Qualitative analysis will include a grounded theory evaluation of responses to open-ended questions regarding adherence to behavioral treatment referral.

### **Data Storage and Confidentiality**

Data from the questionnaires will be entered into REDCap. The questionnaires will be stored in a locked cabinet in the new office [name] will be in as part of the Department of Neurology on [name], in a locked cabinet later on in [name] private outpatient office, and in a locked cabinet in the Men's Health Center Headache Center Office. Any emails sent from the provider to the PI or research volunteer (to be added at a later date) about any study participants needing follow-up telephone calls will be sent via the HIPAA compliant NYUMC webmail system to only those with an NYU email address.

## **Risk/Benefit Assessment**

### **Risk**

There is minimal harm in asking patients about their thought processes regarding behavioral treatments for migraine, which have very minimal risk to patients. Patients do not need to answer any questions which may cause anxiety or discomfort.

Breach of confidentiality is also a risk, which will be minimized by use of the NYU email system only and by use of REDCap.

### **Protection Against Risks**

As stated above, data will be appropriately secured. Patients will be instructed that they can leave the study at any time.

## **Potential Benefits to the Subjects**

Patients may reconsider the possibility of doing evidence based behavioral treatment for their headaches.

## **Investigator's Qualifications & Experience**

Please see the attached CV.

## **Subject Identification, Recruitment and Consent/Assent**

### **Method of Subject Identification and Recruitment**

Patients will be recruited from the New York University Medical Outpatient Setting during their standard Neurology medical appointment (in the FGP Neurology Group by neurologists who have large headache practices, in the private practice office, and Men's Health Center Headache Center).

### **Process of Consent**

MDs (or IRB approved RAs) participating in the study will obtain consent from potential subjects at their Neurology standard medical appointment. Patients will be told that we are doing a study examining their opinions and practices regarding some migraine treatment recommendations. The initial questionnaire is composed of several questionnaires and then there are brief serial follow-up calls in the MI group and one call in the TAU group. Participation is voluntary and will not affect their care whether or not they elect to participate in the study. If patients are uncertain and want to think about it, they can decide to come back within 48 hours to complete the study questionnaire.

In those ages 16-17, the patient will be provided with the consent form along with the parent due to the age of the child. The purpose of the study, risk, benefits, description of the study, subjects right to withdraw and confidentiality will be discussed with the all subjects before consent is obtained.

Subjects will be given an opportunity to ask questions and have their questions answered. Once the subject signs consent the subject will receive a copy of the signed consent form.

To monitor for treatment fidelity, we are requesting to record phone conversations during which motivational interview techniques are employed. The PI will be reviewing these recordings to account for consistency across interviewers. An A/V consent form has been submitted.

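### Two sections give conflicting follow-up schedules (months 1, 2 and 3 for everyone, or one undated TAU call), and follow-through has no stated time point

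*Combined protocol and SAP*

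**What the plan says.** Four places in the combined protocol and SAP bear on this.

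- **Methods & Procedures** makes no distinction by group: "Participants will be told that they will receive a series of follow up calls or REDCap emails regarding their treatment", and "Ten call attempts will be made for each participant for each f/u period (month 1, month 2, month 3". People who cannot be reached are emailed to arrange a call or sent the survey through REDCap, with one repeat. At the clinic visit only the referral itself is recorded. The section points to material outside this file: "Separate documents include scripts of any messages or emails for subjects".
- **Process of Consent** tells patients to expect "brief serial follow-up calls in the MI group and one call in the TAU group". It gives neither the number of MI calls nor the month of the TAU call. It adds: "To monitor for treatment fidelity, we are requesting to record phone conversations during which motivational interview techniques are employed".
- **Analysis Plan** states the comparison: "We will evaluate differences between people who did and did not follow through on behavioral treatment referrals". It gives no window and names no deciding contact. On power it says: "Power analysis suggests we have a power of .80 to detect a medium effect size", two-sided at .05.
- **Study Design** describes one prospective cohort. No section expands the abbreviations MI and TAU, says how a participant enters either group, or plans a comparison between them.

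**The concern.** A TAU participant cannot have both three follow-up periods and one call. This matters because follow-through happens after the visit, so the follow-up contacts are its only described source. If MI participants are asked several times and TAU participants once, someone who starts treatment after the TAU call is never recorded as a starter. That person joins the no-follow-through category. Recorded follow-through then depends partly on group, and the contrast in the Analysis Plan is diluted.

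A second ambiguity is the role of the MI calls. Some of them use motivational interviewing, and the text does not say whether they deliver the intervention, collect the outcome, or both. If they do both, the outcome is obtained under different conditions by group even when the calendar is the same.

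**Working it through.** **1. The plan's own power figure.** It cannot be reproduced exactly, because the numerical effect size, the split and the analysed number are not given. It is attainable. Taking medium as d = 0.5 (assumed) and the 200 expected referrals from Number of Subjects, split 40 against 160, the normal approximation gives 0.5 × √(40 × 160 / 200) − 1.96 = 2.828 − 1.96 = 0.868, so power is about 0.807. This point does not dispute the .80.

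**2. Inputs for the illustration.** From the documents: 200 referrals, contacts at months 1, 2 and 3, two-sided alpha .05. Assumed, and not in the documents:
- cumulative initiation c1, c2, c3 = 10%, 20%, 30% by months 1, 2, 3, the same in both groups;
- 100 people per group, with MI contacted at all three months;
- probability r = 60% or 90% of being reached in each period, independent between periods;
- unreached people counted as not following through;
- d = 0.5 in a continuous variable.

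**3. Recorded follow-through.** With three contacts, S = c1[1 − (1 − r)³] + (c2 − c1)[1 − (1 − r)²] + (c3 − c2)r.
- r = 0.6: 0.0936 + 0.0840 + 0.0600 = 0.2376.
- r = 0.9: 0.0999 + 0.0990 + 0.0900 = 0.2889.

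With one call at month m, the recorded proportion is c_m × r: 6% / 9% at month 1, 12% / 18% at month 2 and 18% / 27% at month 3 (pairs are reach 60% / 90%).

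**4. True starters in the no-follow-through category.** There are 60 true starters among the 200. Recorded = 100 × (MI + TAU proportions), missed = 60 − recorded, and share = missed / (200 − recorded).

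**5. Power.** Everyone recorded as a starter is one, so only the other category is contaminated and the observed difference is 0.5 × (1 − share). Power is from a two-sided two-sample t-test with group sizes recorded and 200 − recorded. With no misclassification (60 against 140) it is 0.897.

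| Schedule | Share, r = 60% | Share, r = 90% | Power, 60% / 90% |
|---|---|---|---|
| Three contacts for all | 12.48/152.48 = 8.2% | 2.22/142.22 = 1.6% | 0.785 / 0.881 |
| One TAU call, month 1 | 30.24/170.24 = 17.8% | 22.11/162.11 = 13.6% | 0.540 / 0.663 |
| One TAU call, month 2 | 24.24/164.24 = 14.8% | 13.11/153.11 = 8.6% | 0.632 / 0.778 |
| One TAU call, month 3 | 18.24/158.24 = 11.5% | 4.11/144.11 = 2.9% | 0.716 / 0.866 |

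**6. Sensitivity to the assumptions.**
- Earlier initiation (25/28/30%, also assumed), r = 0.9, month-1 TAU call: MI 0.24975 + 0.0297 + 0.018 = 0.29745 and TAU 0.225. Recorded 52.245, missed 7.755, share 7.755/147.755 = 5.2%, power 0.834.
- If the same people are always unreachable, a month-3 TAU call gives the same share as three contacts for all (14.6% / 4.1%); a month-1 call gives 20.5% / 14.6%.
- Counting only people who were reached, the share is 6.2% / 1.5% with three contacts for all, 13.2% / 12.6% with a month-1 call and 3.9% / 0.8% with a month-3 call.

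**The case against.** The harm needs several unstated conditions. The consent-section schedule must govern outcome collection rather than merely describe participant burden. For the larger values, the TAU call must also come before month 3. The size then depends on how unreached people are classed. A reasonable alternative reading is that the serial MI calls deliver the intervention and the TAU call is one endpoint contact; at month 3 with high reach the effect is small or nil. The attached questions and scripts, not supplied here, may fix the item and its timing. The initiation curve is assumed, and step 6 shows that it drives the result. All of this stands, and it limits the claim about size. It does not remove the conflict between the two sections, which attachments would not resolve either.

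A reader might infer that the plan contains a biased MI-versus-TAU comparison. With everyone reached, a month-1 TAU call would show a spurious gap of 30% − 10% = 20 points. The documents do not support that reading: the Analysis Plan writes no such comparison and the groups are undefined.

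A reader might also infer that ascertainment is equal for everyone once the Methods schedule applies. That does not follow if motivational-interviewing calls double as outcome contacts.

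**Conclusion.** The point holds in limited form and should be fixed. Confidence is high that the two sections conflict for TAU and that the text gives no time point for follow-through. Confidence is low about the size of any bias.

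Under the base assumptions, a month-1 TAU call raises the contaminated share from 8.2% / 1.6% to 17.8% / 13.6% and lowers power by 0.245 / 0.218. A month-3 call costs 0.069 / 0.015. With early initiation and high reach, even a month-1 call leaves power at 0.834. The documents do not show which of these cases applies, and they do not establish that any bias has occurred.

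**What to change.** - Reconcile Methods & Procedures and Process of Consent. Collect outcome data at months 1, 2 and 3 for all participants, with the same item, contact effort and rule for unreached people.
- In the Analysis Plan, define follow-through as initiation by month 3.
- Define MI and TAU. State whether the MI calls are intervention contacts, outcome contacts or both, and ask the same standard outcome item in every group. Answers already given in MI calls need not be discarded.
- For completed follow-up, report the number and timing of contacts by group.

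Classing as unknown those not recorded as starters and not reached at month 3 is not a dependable remedy. Its power of 0.781 / 0.879 holds only if everyone had the three-contact schedule. With a month-1 TAU call no TAU participant is contacted at month 3, and power is 0.539 / 0.673, close to the 0.540 / 0.663 without the rule. Omit it, or state that limit.

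**Cost.** If the Methods schedule already governs, the change is wording. Otherwise it is two further brief contact periods per remaining TAU participant, which Methods & Procedures already promises. Number of Subjects expects 200 referrals and reports about 150 by 12/10/19. With the remaining 50 split equally (assumed), that is 25 × 2 = 50 periods, at most 50 × 10 = 500 call attempts. Extra contacts may themselves prompt some starts; Potential Benefits to the Subjects says "Patients may reconsider the possibility of doing evidence based behavioral treatment for their headaches".

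Completed follow-up cannot be repaired. If the first 150 had a month-1 TAU call and only the last 50 the full schedule, the base-case share falls only from 17.8% / 13.6% to 15.6% / 10.9%.
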